**Lumbar Imaging with Reporting of Epidemiology (LIRE) Statistical Analysis Plan Revisions**

The following table includes amendments to our statistical analysis plan (SAP) that we included in statistical models for the manuscript but that we did not specify in our original SAP.

Amendments to Statistical Analysis Plan (SAP)	
Number of clinics	

 
• 110 to 98 clinics
 
	When we wrote the SAP we estimated that we would have 110 clinics participating in the trial. We dropped ten clinics prior to randomization for logistical reasons. We dropped two additional small clinics just after randomization and before the first data submission: one had closed and the other had been subsumed in another clinic.
Covariates	We made all decisions regarding covariates before we began the statistical analysis.
Covariates added	Rationale

 
• Site by time interactions
 
	Allow for differential time trends by site

 
• Gender
 
	Allow for outcome differences by gender (precision)

 
• Charlson Comorbidity Index category
 
	Comorbidity measures are associated with outcomes. We sought greater precision by including this general measure of health.

 
• Prior opioid status (opioid models only)
 
	Allow for differences in outcome between those without and those with prior opioid prescriptions (precision)
Covariates transformed	

 
• Time
 
	The SAP and protocol paper indicated that we would model time linearly as 6-month time period (t = 0, 1, 2, 3, 4, 5). Upon further thought, we decided that a more granular measure (i.e. day) would be more appropriate.

 
• Clinical importance of imaging findings
 
	To assess the impact of image findings on the treatment effect, the SAP and protocol paper specified that a binary measure indicating the presence of a clinically important finding would be used. We instead decided to use a three-category measure so that we could measure effect modification among the following groups: patients with likely clinically important findings, patients without likely clinically important findings but with one of the findings included in the LIRE intervention text, and patients without either of these types of finding.

Lumbar Imaging Reporting with Epidemiology (LIRE)  
STATISTICAL ANALYSIS PLAN

Outcomes	

• Opioid prescriptions

	The original SAP defined the opioid outcome as a binary indicator of opioid prescriptions within 90 days, which is the same outcome that we use in the manuscript. When we were writing the protocol paper we thought that morphine equivalent dose (MED) would be more sensitive to the intervention since it could capture reductions in the amount of opioids within prescriptions. However, we discovered that some sites had high missingness for prescription characteristics that we needed to calculate MED. We also encountered challenges identifying duplicate prescriptions. We concluded that it would be better to revert to our original opioid measure for which we would have considerably greater accuracy.

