4.3 Inclusion and Exclusion Criteria

We will define a clinic as a primary care clinic if a majority of the practitioners at that clinic are providing

primary care. We will include general internal medicine and family practice physicians as primary caregivers as well as mid-level providers working with physicians such as nurse practitioners and physician assistants.

We will include all adult patients of eligible caregivers who have had a lumbar spine imaging study (plain film, CT or MR) ordered by their primary care practitioner.

5. Research Design and Methods

[figure not shown]

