7.2 Research Data

Research data will consist of individual subjects' medical record data and information on clinics and providers. We will collect all data passively with automated data extractions. Data extracted from the medical record will include demographic data, variables related to imaging, pharmacy, procedures, hospitalizations, and other factors related to healthcare utilization. We will not collect patient reported outcomes unless they are part of the medical record.

We will collect demographic data on primary care providers and will code the data in such a way that an individual practitioner is not identifiable. We will use patient data to derive pre and post randomization rates of spine related interventions (diagnostic imaging, opioid prescriptions, spine related procedures, physical therapy etc.) among a provider's patient panel.

We will code with a unique study identification number, without reference to patient or provider identity. The code key will be kept secured at the recruitment site, separate from the data. Only the site researchers will have access to the code key (not the researchers at the DCC).

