**Primary Analysis:** The primary longitudinal model for back pain specific RVUs will use a time-varying intervention status indicator  $Status_{kt}$  (0 = control, 1 = intervention, for clinic  $k$  at time  $t$ ). Use of the time-dependent intervention status indicator permits both within-clinic contrasts that inform intervention effects (post-versus pre-intervention) as well as contrasts across clinics with different intervention statuses within each time period. The specific regression model will adopt a functional form given below, with fixed effects for time (linear), age (18-39, 40-59, 60+, using two dummy variables), imaging modality type (plain film, CT, MRI using two dummy variables), and clinic size (small, medium, large, using two dummy variables), and site (Group Health Cooperative, Henry Ford, Kaiser Permanente, Mayo Clinic, using three dummy variables) in addition to random

Lumbar Imaging Reporting with Epidemiology (LIRE)  
 STATISTICAL ANALYSIS PLAN

effects for provider, clinic, and intervention status:

[figure not shown]
$$Y_{ijk} = \beta_0 + \beta_1 \cdot Time_t + \beta_2^T \cdot Age_{ijk} + \beta_3^T \cdot Modality_{ijk} + \beta_4^T \cdot Size_k + \beta_5^T \cdot Site_k + \lambda_0 \cdot Status_{kt} + \quad \text{mean model}$$

$$b_{k,0} + b_{k,1} \cdot Status_{kt} + \quad \text{clinic random effects}$$

$$a_{jk,0} + e_{ijk} \quad \text{provider random effects and errors}$$

We will collect the outcome measure  $Y_{ijk}$  on patient  $i$  ( $i=1,2,\dots,n_j$ ) under primary care provider  $j$  ( $j=1,2,\dots,n_k$ ) enrolled in time period  $t$  ( $t=0,1,2,\dots,5$ ) in order to evaluate the overall effect of the intervention at the level of the clinic  $k$  ( $k=1,2,\dots,110$ ). Note that we will collect a single outcome measure for each subject recording the total utilization (RVU) over the 12 months after the index imaging event. Given that the random effects structure may contain additional elements (see below) we will use a robust standard error to test the null hypothesis that  $\lambda_0 = 0$ . For example, using SAS PROC MIXED we can use the “empirical” option in order to obtain robust standard errors. Alternatively, use of the jackknife (at the clinic level) provides a robust standard error estimate (if using R and *lmer*) that is simple to compute.

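### The primary RVU and re-imaging models omit the patient's own prior spine care, which gives up precision but does not bias the intervention effect

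*SAP*

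**What the plan says.** **Primary model.** The SAP's Primary Analysis section specifies "fixed effects for time (linear), age (18-39, 40-59, 60+, using two dummy variables), imaging modality type (plain film, CT, MRI using two dummy variables", together with clinic size, site and intervention status, and random "effects for provider, clinic, and intervention status". The outcome is one value per patient, "recording the total utilization (RVU) over the 12 months after the index imaging event".

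**Revisions.** The SAP Revisions table adds site-by-time interactions, gender and Charlson category. It also adds "Prior opioid status (opioid models only"), with the rationale "Allow for differences in outcome between those without and those with prior opioid prescriptions (precision". Charlson category is justified in the same way: "We sought greater precision by including this general measure of health". The table states that covariate decisions were made before the statistical analysis started.

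**Re-imaging.** Under Secondary Outcome Analysis, the SAP gives Aim 1c a binary outcome (CT or MR within, for example, 90 days or 12 months) in a model that parallels the primary one. Protocol 5.7, Aim 1c, mentions a random effect for the baseline re-imaging rate. That is not a patient's own imaging history.

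**Population and data.** Protocol 4.3 sets broad entry: "We will include all adult patients of eligible caregivers who have had a lumbar spine imaging study". There is no exclusion for recent spine care or earlier imaging. Protocol 7.2 lists the extracted data as including "variables related to imaging, pharmacy, procedures, hospitalizations, and other factors related to healthcare utilization".

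**The concern.** A patient may enter the trial with a first image, or with an image taken in the middle of injections, physical therapy or surgical work-up. For the second kind of patient, part of the following year's RVU, and perhaps a repeat MR, comes from care already under way. That difference between patients adds noise to the endpoint, and no term in the RVU or re-imaging model measures it at patient level. Charlson category is a general health index. Modality is at most a loose proxy for stage of care. Clinic and provider random effects absorb only differences between clusters.

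The plan accepts the argument for opioids, where baseline status goes into the model for precision, but does not carry it to the primary endpoint. At stake is the width of the primary confidence interval and the sharpness of the Aim 2 and Aim 3 interaction tests, for which the SAP gives no power figure.

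**Working it through.** **1. Covariates side by side**

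- RVU model (Primary Analysis plus Revisions): time, age, modality, clinic size, site, status, site-by-time, gender, Charlson category. Prior spine care: none.
- Re-imaging model (parallel to the RVU model): the same list. Prior lumbar imaging: none.
- Opioid model: the same list plus prior opioid status. Protocol 5.7, Aim 1b, also plans separate analyses by active prescription at baseline.

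**2. Where the variance lies**

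SAP, Power for Primary Outcome: clinic 0.026 and residual 1.230 on log(RVU + 1). The share below clinic level is 1.230 / (1.230 + 0.026) = 97.9%. The same components give an ICC of 0.026 / 1.256 = 0.021, whereas the SAP states 0.013. On either value, about 98% to 99% of the variance is below the clinic. The SAP says that this residual also contains provider variance.

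**3. Reproducing the plan's power**

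The SAP states more than 90% power for a 5.0% reduction in median RVU.

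- Effect: δ = −ln(0.95) = 0.0513.
- Design: 110 clinics with sizes approximated from SAP Table 1 (1,824 PCPs), 6 periods, 5 waves, random clinic intercept, generalised least squares variance for a stepped wedge.
- Patients: about 100,000 anticipated in the protocol, so 100,000 / (1,824 × 6) = 9.1 per PCP per period.
- Two-sided α = 0.05 (assumed, since the SAP does not state it).
- Power = Φ(δ/SE − 1.96).

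Without the three-month washout, SE = 0.0124 and power is 98.5%. With washout, SE = 0.0137 and power is 96.2%. The stated figure is consistent with this. It depends on the patient count, for which the SAP gives no per-PCP figure: at 5 patients per PCP per period, power is 87% without washout and 80% with it.

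**4. Adding a prior-care covariate**

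Let R² be the share of patient-level residual variance that the covariate explains. The documents give no value, so the range is an assumption. The residual becomes 1.230 × (1 − R²), and SE falls by roughly 1 − √(1 − R²). With washout and site-by-time terms:

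| R² | 1 − √(1 − R²) | SE | Power for 5% | Reduction detectable at 90% power |
|---|---|---|---|---|
| 0 | – | 0.0137 | 96.2% | 4.35% |
| 0.05 | 2.5% | 0.0134 | 96.9% | 4.25% |
| 0.10 | 5.1% | 0.0131 | 97.6% | 4.14% |
| 0.20 | 10.6% | 0.0123 | 98.6% | 3.92% |
| 0.30 | 16.3% | 0.0116 | 99.3% | 3.68% |
| 0.40 | 22.5% | 0.0107 | 99.8% | 3.41% |

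The last column is 1 − exp(−SE × (1.96 + 1.28)).

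**5. If the effect varies between clinics**

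The primary model has a random intervention effect, while the SAP describes its power simulations as random-intercept models. With an illustrative effect variance of 0.006 (not in the documents), SE is 0.0166 without the covariate. It becomes 0.0160, 0.0154 and 0.0140 at R² = 0.10, 0.20 and 0.40. That is a fall of 3.6%, 7.2% and 15.7%, smaller than in step 4. Power goes from 87.1% to 89.3%, 91.5% and 95.5%.

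All of this uses 110 clinics. The final 98 would lower power somewhat. The SAP gives no power figure for re-imaging, so nothing was recomputed for Aim 1c.

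**The case against.** The strongest case against is that this is a preference and not an error. The stepped-wedge order is randomised, and time (by day in the Revisions) and site-by-time are modelled, so the model is valid without one more prognostic covariate. That stands. A reader might infer that the omission biases the effect through drift in the mix of new and ongoing patients. The documents offer no evidence of such drift beyond what the time terms, modality, age, gender and Charlson category absorb.

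A reader might also infer that the missing covariate is why the RVU mixes continuing with new care. It is not. The mixing comes from the outcome definition and the deliberately broad eligibility. A covariate reduces the noise from it but does not split the two, which would need a subgroup or interaction by prior care.

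Three further points stand in part:

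- The gain is uncertain. R² is assumed, and some of the 1.230 is provider variance that a patient covariate need not reduce. With power already near 96%, the benefit is mostly a narrower interval.
- The opioid models have a documented reason of their own: some patients already hold a prescription at the index visit. But the rationale recorded in the Revisions is precision, and that reason is not specific to opioids.
- The documents specify no 12-month look-back, and Protocol 5.4 describes baseline data at clinic level. Prior opioid status nevertheless requires some patient-level records from before the index image.

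**Conclusion.** The omission is real: neither the RVU model nor the re-imaging model uses the patient's own spine care before the index image, although the plan's stated reason for the opioid covariate applies to both. The consequence is lost precision, not bias. For R² of 10% to 40%, the standard error of the RVU effect would be about 5% to 22% smaller, and the reduction detectable at 90% power would move from 4.35% to between 4.14% and 3.41%.

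These figures rest on the assumed R², about 100,000 patients, 110 clinics, two-sided α of 0.05, and a residual treated as wholly patient-level. Provider variance in that residual, or between-clinic variation in the effect, would shrink the gain. This is a cheap improvement, and the existing primary analysis remains valid without it.

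**What to change.** - **RVU model:** add log(spine-related RVU + 1) over the 12 months before the index image. Use the existing CPT and diagnosis algorithm, which the SAP's Primary Outcome section says already aggregates RVUs per patient over a time interval.
- **Aim 1c models:** add an indicator of lumbar CT or MR before the index image.
- **Both:** add an indicator for incomplete look-back, and report the model without prior care alongside.
- **Timing:** specify this before outcome analysis. If analysis has begun, keep the pre-specified model as primary and label the adjusted one supportive.

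**Cost:** SAP wording and a derived look-back variable per patient, with no new patients or procedures. The look-back window has to be defined, and some histories will be incomplete. In the logistic re-imaging model, adjustment also changes the conditional odds ratio, so the two versions do not estimate the same quantity and should not be compared as if they did.
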